8.7.2 Safety analysis

- ① Among the subjects of safety evaluation, the number of subjects with adverse event incurred and the number of adverse events incurred should be calculated, and the incidence rate of adverse events and the 95% confidence interval should be presented.
- ② The number and percentage of adverse events by type and category should be presented.
- 3 Analysis should be made using Chi-square test or Fisher's Exact test on the adverse event onset status by demographic data of subjects of safety evaluation.

Proprietary confidential information © 2017 Boehringer Ingelheim International GmbH or one or more of its affiliated companies

④ To estimate any factors that are thought to influence the analyzed incidence rate of adverse events, logistic regression analysis should be conducted, and for statistically significant parameters, the meaning should be described.

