4. ABSTRACT

| Name of company: | | | |
|--|---|-------------------|------------------------|
| Boehringer Ingelheim Korea | | | |
| Name of finished medicinal product: JARDIANCE® | | | |
| Name of active ingreempagliflozin | edient: | | |
| Protocol date: | Study number: | Version/Revision: | Version/Revision date: |
| 27 May 2016 | 1245.116 | 6.0 | 23 Nov 2017 |
| Title of study: | A regulatory requirement non interventional study to monitor the safety and effectiveness of JARDIANCE® (empagliflozin, 10mg, 25mg) in Korean patients with type 2 diabetes mellitus | | |
| Rationale and background: | According to the local regulations, when a new chemical entity (NCE) is registered, a regulatory non interventional study (NIS) of an extended period (6 years) should be conducted. A rNIS can provide supplementary data to monitor the safety of NCEs in a real-life situation. Data collected in randomized clinical study with strict inclusion/exclusion criteria and rigorous monitoring schemes have limitations. | | |
| Research question and objectives: | To monitor the safety profile and efficacy of JARDIANCE® (empagliflozin, 10mg, 25mg) in Korean patients with type 2 diabetes mellitus in a routine clinical practice setting | | |
| Study design: | Observational prospective, non-interventional, open-label, multi-centre study | | |
| Population: | Patients diagnosed with type 2 diabetes mellitus in Korea Inclusion criteria: Patients who have started at first time on JARDIANCE® in accordance with the approved label in Korea Age ≥ 19 years at enrolment Patients who have signed on the data release consent form Exclusion criteria: Known hypersensitivity to empagliflozin or any of its excipients Patients with type 1 diabetes or for the treatment of diabetic ketoacidosis Patients with persistent eGFR<60 mL/min/1.73 m²,end stage renal disease or on dialysis Patients with rare hereditary conditions of galactose intolerance, the Lapp lactase deficiency or glucosegalactosemalabsorption Patients for whom empagliflozin is contraindicated according local label of JARDIANCE® | | |
| Variables: | Endpoints of safe | ety | |

| Name of company: | | | |
|--|--|---|---|
| Boehringer Ingelheim Korea | | | |
| Name of finished medicinal product: JARDIANCE® | | | |
| Name of active ingrempagliflozin | edient: | | |
| Protocol date: | Study number: | Version/Revision: | Version/Revision date: |
| 27 May 2016 | 1245.116 | 6.0 | 23 Nov 2017 |
| | JARDIANCE® v | | at least one dose of |

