8.1.2 Dosage and Administration

The starting dose and the dose escalation schedule are based on the current authorized label in Korea.

The recommended dose of JARDIANCE[®] is 10 mg once daily. In patients tolerating JARDIANCE[®] 10 mg once daily and requiring additional glycemic control, the dose can be increased to 25 mg once daily.

When JARDIANCE[®] is used in combination with a sulphonylurea or with insulin, a lower dose of the sulphonylurea or insulin may be considered to reduce the risk of hypoglycaemia.

Proprietary confidential information © 2017 Boehringer Ingelheim International GmbH or one or more of its affiliated companies

JARDIANCE[®] can be taken with or without food and tablets should be swallowed whole. If a dose is missed, it should be taken as soon as the patient remembers. A double dose should not be taken on the same day.

Please refer to the current local label for about Special populations (*Patients with renal impairment, Patients with hepatic impairment, Elderly patients*).

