8.7 DATA ANALYSIS

8.7.1 Analysis of demographic data

Demographic data and the health status of subjects for the safety evaluation will be analysed descriptively. For continuous data, mean, standard deviation, minimum value, and maximum value will be described, while for categorical data, frequency will be shown.

Parameters corresponding to demographic data are as mentioned below.

- Basic information and disease information
 Age, gender, pregnancy, body weight, smoking status, diabetes mellitus
 complications, other medical history, disease period, Family history of T2DM,
 elderly (Age ≥ 65 years), renal impairment and hepatic impairment, allergy, long
 term use(over 24 weeks)
- ② Medication information Concomitant medication, study drug administration status (total period of drug use, average of daily dose), reason for early interruption, any anti-diabetic agents

To assess the extent of preferential prescribing and the potential for channeling bias, data from the TRAJENTA® (linagliptin) rPMS will be used as a comparator. The baseline characteristics of patients starting JARDIANCE® for the first time will be compared to the baseline characteristics of patients who started TRAJENTA® for the first time. Proportions and means (SD) of the baseline characteristics will be compared using absolute standardized differences (ASD), where an ASD of at least 10% will be considered a meaningful difference. p-values will also be calculated.

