8.7.2.1 Adverse Events by preferred Terms (AEs/ADRs/SAEs)

All AEs recorded in the CRF will be classified by body organs and terms under the classification standard of MedDRA terms, and all AEs excluding the AEs whose 'Causality' is "Unlikely" will be treated as AEs whose causality cannot be excluded (hereafter "Adverse Drug Reaction (ADR)"). The study database will not be locked until coding is complete.

- The number of AE according to Severity (Mild, Moderate, Severe), Outcome of the event (Recovered, Not yet recovered, Sequelae, Fatal, Unknown), Action taken with trial drug due to AE (Continue, Reduced, Discontinued, Increased, Discontinued and reintroduced, Not applicable), Causality (Certain/ Probable·Likely/ Probable/ Possible/ Unlikely/ Conditional· Unclassified/ Unaccessible·Unclassifiable), Therapy for the event (Yes, No) will be calculated.
- ② All AEs will be classified into the preferred terms according to Severity (Mild, Moderate, Severe), Outcome of the event, (Recovered, Not yet recovered, Sequelae, Fatal, Unknown), Action taken with trial drug due to AE (Continue, Reduced, Discontinued, Increased, Discontinued and reintroduced, Not applicable), Causality (Certain, Probable/Likely, Possible, Unlikely), Therapy for the event (Yes, No). Also, the number of each AE will be calculated.
- The number of patients and the number of Serious AE/Serious ADR (SADR), unexpected AE/ADR, unexpected Serious AE/unexpected Serious ADR, AE/ADR will be calculated according to the preferred terms. Also, the incidence proportion and its 95% confidence interval will be estimated.
- Tor subjects excluded from safety analysis set [‡], the number of patients and the number of Serious AE/Serious ADR (SADR), unexpected AE/unexpected ADR, unexpected Serious AE/unexpected Serious ADR, AE/ADR will be calculated according to the preferred terms. Also, the incidence proportion and its 95% confidence interval will be estimated.

‡Patients excluded from safety analysis sets: 'Patients who have not taken JARDIANCE[®]' and 'Follow-up failure' of patients excluded from safety analysis sets will be excluded (This term reflects the Ministry of Food & Drug Safety (MFDS) guideline).

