Medical judgment should be used to determine the relationship, considering all relevant factors, including pattern of reaction, temporal relationship, de-challenge or re-challenge, confounding factors such as concomitant medication, concomitant diseases and relevant history.

Arguments that may suggest a reasonable causal relationship could be:

- The event is consistent with the known pharmacology of the drug
- The event is known to be caused by or attributed to the drug class.
- A plausible time to onset of the event relative to the time of drug exposure.
- Evidence that the **event is reproducible** when the drug is re-introduced
- No medically sound alternative etiologies that could explain the event (e.g. preexisting or concomitant diseases, or co-medications).
- The event is typically **drug-related and infrequent in the general population** not exposed to drugs (e.g. Stevens-Johnson syndrome).
- An indication of dose-response (i.e. greater effect size if the dose is increased, smaller effect size if dose is diminished).

Arguments that may suggest that there is **no reasonable possibility of a causal relationship** could be:

- No plausible time to onset of the event relative to the time of drug exposure is evident (e.g. pre-treatment cases, diagnosis of cancer or chronic disease within days/weeks of drug administration; an allergic reaction weeks after discontinuation of the drug concerned)
- Continuation of the event despite the withdrawal of the medication, taking into account the pharmacological properties of the compound (e.g. after 5 half-lives). Of note, this criterion may not be applicable to events whose time course is prolonged despite removing the original trigger.
- Additional arguments amongst those stated before, like alternative explanation (e.g. situations where other drugs or underlying diseases appear to provide a more likely explanation for the observed event than the drug concerned).
- Disappearance of the event even though the study drug treatment continues or remains unchanged.

The causal relationship must be provided by the Investigator for all potential study drugs, i.e. the BI study drug and for all other study drugs.

The reason for the decision on causal relationship needs to be provided in the (e)CRF and on the NIS AE form (if applicable).

Related

a. Certain: An event occurring in a plausible time relationship to drug administration and that cannot be explained by concurrent disease or other drugs or chemicals. The

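### The only dose factor named for the adverse event analysis is whole-period average daily dose, which mixes doses before and after the event and partly depends on the outcome

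*Protocol*

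**What the plan says.** The abstract (section 4) describes the product under study as "JARDIANCE® (empagliflozin, 10mg, 25mg) in Korean patients with type 2 diabetes mellitus". Section 8.1.2 gives 10 mg once daily as the recommended dose and says that, in patients who tolerate it and need more glycaemic control, "the dose can be increased to 25 mg once daily".

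The safety analysis has three relevant parts.

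- Section 8.7.2, item 1: for the safety population, "the incidence rate of adverse events and the 95% confidence interval should be presented". Section 8.7.2.1 adds, by preferred term, that "the incidence proportion and its 95% confidence interval will be estimated". Neither has a dose breakdown.
- Section 8.7.2, item 3: AE occurrence is tested by chi-square or Fisher's exact test against the demographic data. Item 4 adds a logistic regression on influencing factors, which it does not list.
- Section 8.7.1 defines those data with the sentence "Parameters corresponding to demographic data are as mentioned below". The list that follows includes, as medication information, "study drug administration status (total period of drug use, average of daily dose". No other dose variable is named for analysis.

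The data collected are richer. Daily dose with its start date is recorded at baseline, and any change is recorded at Visits 2 and 3 (8.2.3.2 to 8.2.3.4). AE onset date is recorded (8.3.3.1) and is marked as mandatory in the source data list (8.10.2.1).

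**The concern.** Read together, 8.7.1 and 8.7.2 item 3 make average daily dose the factor against which AE occurrence is compared. It is a poor exposure measure here for two reasons.

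First, it looks past the event. An event in week 6 on 10 mg and one in week 18 on 25 mg get the same dose value if both patients escalated at week 12.

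Second, it depends on the outcome. Escalation under 8.1.2 is for patients who tolerate 10 mg, so an early AE can keep a patient at a low average. Sections 8.3.3.1 and 8.7.2.1 also list dose reduction, increase and discontinuation as actions taken because of an AE, so the average can be a consequence of the event.

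Safety is the primary objective (7.1). At stake is whether an AE that is more frequent on 25 mg would be seen. With this factor it could be diluted or hidden, and a dose with no effect on the AE rate could look protective.

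**Working it through.** There is no figure in the plan to reproduce: the 3,000 patients in 8.5 follow from a regulatory requirement, without an event rate or precision target. The steps below show how the average behaves.

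**Inputs from the protocol:** doses of 10 mg and 25 mg (8.1.2); 24 weeks of follow-up (8.5).

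**Assumed inputs:** a time-weighted average (the protocol gives no averaging rule); constant event rates; a 24-week AE risk p on 10 mg of 2%, 5% or 10%; a rate ratio RR of 1 or 2 for 25 mg against 10 mg; escalation at week w.

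**1. Average dose of an escalated patient.** Average = (10w + 25(24 − w))/24. At w = 12 this is (120 + 300)/24 = 17.5 mg. For w = 4, 8, 16 and 20 it is 22.5, 20.0, 15.0 and 12.5 mg. None of these is a dose the patient took.

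**2. Events placed under the wrong dose.** The weekly rate on 10 mg is h = −ln(1 − p)/24. With RR = 1, the share of escalated patients' first events that occurred while still on 10 mg is (1 − exp(−hw))/p. This is about 17% for w = 4, 50% for w = 12 and 83% for w = 20. All of these events are counted under an average above 10 mg.

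**3. Dilution when escalation ignores events.** The risk of an escalated patient is 1 − exp(−[hw + RR·h(24 − w)]). Take p = 5%, RR = 2 and w = 12. Then h = 0.002137, the exponent is 36h = 0.0769 and the risk is 7.41%. Against 5% for patients always on 10 mg, the ratio is 7.41/5 = 1.48, where the true rate ratio is 2. Over the three values of p:

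| Escalation week | Apparent ratio (true rate ratio 2) |
|---|---|
| 4 | 1.76 to 1.82 |
| 12 | 1.46 to 1.49 |
| 20 | 1.16 |

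**4. Outcome dependence.** Suppose only patients free of the event at week w escalate. Their risk is 1 − exp(−RR·h(24 − w)). With RR = 2 and w = 12 the exponent is 2 × 12h = 24h, the same as 24 weeks on 10 mg, so the ratio is 1.0 and the doubling disappears. With RR = 1 and w = 12 the ratio is 0.50 to 0.51, so a dose with no effect looks protective.

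**5. Precision of a dose-specific figure.** For an assumed 1% event proportion, the exact 95% interval is 0.68% to 1.42% in 3,000 patients, 0.46% to 1.89% in 900 and 0.21% to 2.89% in 300. The strata of 900 and 300 are assumptions. Intervals on exposure time would differ somewhat.

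**The case against.** The strongest reply is that only the protocol is at hand. Further tables by dose, and the categories for average dose, are commonly left to the statistical analysis plan, and the pooled incidence in 8.7.2 item 1 is not wrong. That is fair, and a missing table alone would not be a finding. What remains is that the protocol itself names the dose variable and sends it into the AE tests, so a later plan would have to override that choice rather than fill a gap.

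Several stronger readings are tempting, and the text does not support them.

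- A reader might infer that every AE analysis is pooled over dose. It is not: item 3, through the list in 8.7.1, compares AE occurrence across average dose.
- A reader might infer that an escalated patient is recorded at 17.5 mg. The eCRF holds each dose with its dates; 17.5 mg is only a derived summary.
- A reader might infer that dose comparison is an objective. Sections 7.1 and 7.2 name the product without strengths, and 8.1 describes a single arm. The line in 10.2, "An indication of dose-response (i.e. greater effect size if the dose is increased, smaller effect size if dose is diminished", is one argument for judging causality in an individual case and does not commit the study to a dose-response analysis.
- A reader might take 8.7.2 and 8.7.2.1 to fix pooled incidences of adverse events of special interest (AESIs). Those sections do not name AESIs, which appear as an endpoint in 8.3.2.1.

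Tables by dose at onset have a bias of their own. Time on 25 mg after escalation comes later and from patients who tolerated 10 mg. This stands, and limits the tables to description.

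**Conclusion.** The point holds as a badly chosen exposure measure, and it should be corrected. The named dose factor is a post-baseline average that escalation and AE-driven dose changes can distort. No analysis in the protocol uses the dated dose and onset data to tie events to the dose being taken.

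The size is illustrative only. Under the assumptions above, a true doubling on 25 mg appears as 1.16 to 1.82 depending on when escalation occurs, and as about 1.0 when only event-free patients escalate at week 12. The share of patients on 25 mg, the timing of escalation and the event rates are not in the document, so the actual distortion could be small or large. The conclusion also rests on taking the medication items as demographic parameters, which is how 8.7.1 introduces them.

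**What to change.** - **8.7.1:** add starting dose (category) and dose change (yes/no, with week of change). Keep average daily dose only as a descriptive summary of exposure.
- **8.7.2, item 3:** name starting dose, not average daily dose, as the dose factor.
- **8.7.2 and 8.7.2.1:** add descriptive tables of AEs, adverse drug reactions, serious AEs and AESIs (endpoint in 8.3.2.1) by daily dose at onset (10 mg, 25 mg, other). Use exposure time at that dose as denominator, so that a patient whose dose changed contributes time to each dose.
- State beside the tables that dose is chosen by the physician, and that time on 25 mg after escalation comes later and from patients who tolerated 10 mg. The tables are therefore not a causal comparison of doses.

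The cost is analysis wording and a few tables, with no new data and no change to patient care. The 25 mg intervals may be wide. If nearly all patients start on 10 mg, the starting-dose test will say little and the tables by dose at onset will carry most of the information.

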8.7.3 Efficacy analysis

- Mean, standard deviation, minimum value, maximum value, and median of changes in glycosylated hemoglobin(HbA1c) and fasting plasma glucose(FPG), body weight, and blood pressure (SBP, DBP), which were measured at the last visit versus baseline, should be presented, and if there is difference before administration versus after administration should be analyzed using paired t-test.
- ② If there is difference in the change of glycosylated hemoglobin(HbA1c) according to demographic parameters mentioned in 8.7.1 should be analyzed using t-test or ANOVA(Analysis of Variance).
- The frequency and percentage of patients who had glycosylated hemoglobin(HbA1c) reaching less than 7% (target efficacy response rate) at the last visit should be calculated, and the frequency and percentage of patients with glycosylated hemoglobin(HbA1c) decreased by at least 0.5% at the last visit should be calculated.
- For final efficacy evaluation (improved, unchanged, aggravated, unassessable) and 'effective(improved)'/'ineffective(unchanged, aggravated)', the number and percentage of subjects should be mentioned. The final effectiveness evaluation of "Improved" will be classified as "Effective", "Unchanged" and "Aggravated" will be classified as "Ineffective". The effectiveness rate and its 95% confidence intervals will be estimated with exact method.
- ⑤ To estimate any factors that are thought to influence an effective ratio, logistic regression analysis should be conducted, and for statistically significant parameters, the meaning should be described.

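### The logistic regressions in 8.7.2 and 8.7.3 interpret a factor only if it is statistically significant, with no effect estimate, confidence interval or allowance for the number of parameters examined

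*Protocol*

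**What the plan says.** Section 8.7.2 item 4 introduces a regression with the aim "To estimate any factors that are thought to influence the analyzed incidence rate of adverse events" and then sets the reporting rule: "logistic regression analysis should be conducted, and for statistically significant parameters, the meaning should be described". Section 8.7.3 item 5 does the same for effectiveness, starting from "To estimate any factors that are thought to influence an effective ratio" and ending with the same clause.

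Two neighbouring items compare subgroups one parameter at a time but carry no rule on which results are interpreted:
- 8.7.2 item 3, for adverse events: "Analysis should be made using Chi-square test or Fisher's Exact test on the adverse event onset status by demographic data of subjects of safety evaluation".
- 8.7.3 item 2, for HbA1c change: "according to demographic parameters mentioned in 8.7.1 should be analyzed using t-test or ANOVA".

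The parameters are listed in 8.7.1. The basic and disease list opens with "Age, gender, pregnancy, body weight, smoking status, diabetes mellitus" and includes "renal impairment and hepatic impairment, allergy"; it has 14 entries. The medication list has five more: "Concomitant medication, study drug administration status (total period of drug use, average of daily dose), reason for early interruption, any anti-diabetic agents". The protocol does not say that these 19 are the candidates for the logistic models, and it states no significance level for them.

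**The concern.** The clause is an instruction on interpretation, so an analysis plan that follows the protocol inherits it. A significance filter over many parameters can err in two ways. It can lead the report to explain a factor that is only a chance finding. It can also leave an imprecise result in a small group without comment, and a reader may take that silence as evidence of no added risk. Both matter because monitoring safety is the primary objective (7.1), and 8.2.2.4 singles out older, pregnant, renally impaired and hepatically impaired patients.

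The rule is also out of step with the rest of the protocol. Section 8.7.1 judges baseline differences against the linagliptin survey by an absolute standardized difference of at least 10%, with p-values as an addition. Adverse event incidence and the effectiveness rate are both to be given with 95% confidence intervals. The logistic regressions are given neither an effect-size criterion nor an interval.

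**Working it through.** The protocol has no error rate or power figure to reproduce: 8.5 sets N = 3,000 as a regulatory requirement.

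**Inputs from the protocol.** N = 3,000; k = 14 parameters (basic and disease list) or k = 14 + 5 = 19 (with the medication list).

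**Assumed inputs.** Two-sided alpha of 0.05; all k parameters are candidates; adverse event risk and subgroup sizes as shown below.

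**1. Chance of at least one false factor, per outcome.** With independent tests and no true factor, this is 1 − (1 − alpha)^k.
- k = 14: 1 − 0.95^14 = 0.512; expected false factors 14 × 0.05 = 0.70.
- k = 19: 1 − 0.95^19 = 0.623; expected false factors 19 × 0.05 = 0.95.

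The parameters overlap (age with elderly status, total period of use with long-term use), so correlation was varied:

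| Setting | k = 14 | k = 19 |
|---|---|---|
| Independent | 0.51 | 0.62 |
| Correlation of test statistics 0.1 | 0.50 | 0.61 |
| Correlation 0.3 | 0.44 | 0.53 |
| Correlation 0.5 | 0.35 | 0.41 |
| Overlapping pairs (age/elderly type) | 0.48 | 0.59 |
| Simulated multivariable logistic model, no true factor, 15% event rate | 0.47 | 0.59 |

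Fitting one multivariable model therefore does not remove the problem. The result depends strongly on the unstated alpha: at 0.01 the independent figures are 0.13 and 0.17; at 0.10 they are 0.77 and 0.86.

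**2. Chance of missing a real factor in a small group.** Power of a two-sided 0.05 comparison of n patients with the other 3,000 − n, by normal approximation:

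| Event risk in the rest, risk ratio | n = 30 | n = 60 | n = 150 | n = 600 |
|---|---|---|---|---|
| 5%, 2.0 | 0.30 | 0.44 | 0.71 | 0.99 |
| 10%, 1.5 | 0.19 | 0.28 | 0.50 | 0.92 |
| 10%, 2.0 | 0.46 | 0.67 | 0.93 | 1.00 |
| 20%, 2.0 | 0.73 | 0.94 | 1.00 | 1.00 |

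**3. What the filter would leave out.** Suppose 6 of 30 patients in a small group have an event (20%), against 297 of the other 2,970 (10%).
- Odds ratio = (6/24) / (297/2,673) = 2.25.
- SE of the log odds ratio = √(1/6 + 1/24 + 1/297 + 1/2,673) = 0.461.
- 95% CI = exp(0.811 ± 1.96 × 0.461) = 0.91 to 5.55.

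This is not significant, so the rule calls for no comment. The interval shows that the result is inconclusive and compatible with a large excess.

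**4. Would a multiplicity correction alone help?** Bonferroni over 19 parameters brings the false-factor chance to 0.049. At 10% risk and a risk ratio of 2, however, power falls from 0.46 to 0.18 (n = 30) and from 0.67 to 0.36 (n = 60). Correction alone trades one error for the other.

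**The case against.** Alpha, the covariate list, the form of the model and the layout of estimates commonly sit in a statistical analysis plan, which may exist and is not shown. That stands for each of those details, and their absence is not the point here. The clause tying interpretation to significance is written in the protocol itself.

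Several stronger readings are tempting, and the document does not support them:
- **A p < 0.05 screen over all 14 to 19 parameters.** No alpha is given, the logistic candidates are open-ended, and no selection procedure is described. Reason for early interruption applies only to patients who stopped, so 19 is a generous count.
- **A rule that also governs the univariable tests.** The significance clause is absent from 8.7.2 item 3 and 8.7.3 item 2. HbA1c change is therefore not an outcome of this rule, and a false-factor probability pooled over three outcomes would not measure it.
- **Real risks will be hidden.** Asking for significant parameters to be described does not order the others to be withheld. Item 3 of 8.7.2 still analyses adverse events by demographic data, and 8.2.2.4 leaves room for further investigation of special populations. Group sizes and event rates are not stated, and a large group has ample power (an assumed 600 patients gives 1.00 for a doubled 10% risk).

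The assumption of no true factor is also doubtful, since 6.2 reports more urinary tract infections, especially in women. If one parameter is a true factor, 13 or 18 null parameters remain, and the independent figures become 1 − 0.95^13 = 0.49 and 1 − 0.95^18 = 0.60, which changes little.

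Finally, this is exploratory safety monitoring, where strict error control is a matter of choice. That stands, and it is why no adjustment is required below.

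**Conclusion.** The point holds for the two logistic regressions, 8.7.2 item 4 and 8.7.3 item 5. Statistical significance is the only stated ground for interpreting a factor, and nothing about size, precision or number of parameters accompanies it.

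If alpha is 0.05 and the parameters of 8.7.1 are the candidates, the chance of describing at least one false factor per outcome is about 0.44 to 0.62 under independence to moderate correlation, and 0.35 to 0.41 under strong correlation. Small groups such as hepatic or renal impairment may lack the power to reach significance. With about 60 patients or fewer and an event rate of 10% or lower, a doubled risk would be missed in at least a third of cases (1 − 0.67 = 0.33). Whether those groups will be that small is not stated. This is a reporting rule worth correcting, and it does not invalidate the study's incidence estimates.

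**What to change.** In 8.7.2 item 4 and 8.7.3 item 5, replace the clause on significant parameters with the following:
- Report the odds ratio and 95% CI for every parameter analysed, whatever its p-value.
- Interpret factors by the size and precision of the estimate, and state that a wide interval is inconclusive.
- Label p-values as exploratory and unadjusted, and give the number of parameters tested.

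The same reporting (difference with 95% CI) can be applied to the univariable analyses in 8.7.2 item 3 and 8.7.3 item 2. A false discovery rate adjustment may be added, but it should not be a condition for reporting a possible safety factor, because it lowers sensitivity in the small groups of interest.

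The logistic regressions stay in place, as the amendment log attributes their current form to regulator comments. No new data are needed. The cost is a few extra table columns and more cautious wording.
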